Approximately 4.5 years after baseline 57 premanifest HD gene carriers (89% retention) and 45 healthy controls (67% retention) returned for a follow-up visit (HD-YAS 2.0). An additional 23 new participants were recruited: 9 premanifest HD gene carriers and 14 controls. The full cohort consists of 66 premanifest HD gene carriers and 59 healthy controls, matched for age, gender and education. All participants completed the clinical and cognitive assessments, 91% had MRI and 86% underwent CSF collection. The cohort will be characterised in terms of the new Huntington's Disease Integrated Staging System (HD-ISS) (Tabrizi *et al*, 2022), which incorporates disease pathology and biomarkers within staging classification. In addition, predicted years to clinical onset will be linked to standardisation of the CAG-Age-Product (CAP) score via previously described statistically modelling of CAP=100 at the expected age of diagnosis (Warner *et al*, 2022). These measures will be important for disease staging in future clinical trials.

General Methods

Measures

Approximately 70 individual variables from various measurement domains will be

analysed as outcome variables that may differ between the premanifest HD gene carriers and controls. The majority of measures are identical to baseline, with a few exceptions:

- One cognitive task, the breakpoint assessment, was removed from the battery due to feedback from participants. A novel task, The Goals Prior Assay, was introduced to capture the motivational domain.
- Neurogranin, a marker of synaptic function, was not assessed at this timepoint. There was no significant difference in CSF neurogranin concentration between the premanifest HD gene carrier and control groups at baseline in HD-YAS.
- Total huntingtin (tHTT) was not assessed at this timepoint. At baseline, the presence of the mutant HTT gene did not have any effect on tHTT concentrations; tHTT concentrations in CSF were unchanged in premanifest HD gene carriers.
- Volumetric neuroimaging measures, in addition to cross-sectional measures at this timepoint, include a direct measure of change, the boundary shift integral (BSI). This method has shown greater sensitivity to subtle longitudinal volumetric change than independent volume measures at each timepoint (Freeborough and Fox).
- We have included a measure of CAG-repeat expansion derived from blood DNA. This will be assessed using both the HD-YAS 1.0 and HD-YAS 2.0 samples.

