Violation of model distribution assumptions

For the default general linear models, the key standard assumptions are that residuals of the outcome variable will be approximately normally distributed, independent of the predicted values, and with uniform variance. The assumption is most commonly violated when the residuals show notable skewness. In such cases we will first evaluate whether the assumptions are reasonably satisfied by a square-root, log, polynomial, or inverse

transformation of the outcome, in which cases the analysis will proceed with the transformed variable. Such transformations are most commonly unsatisfactory due to floor or ceiling effects in the range of measurement of the outcome. In such cases we will consider the feasibility of using an ordinal logistic model or a censored model. If neither of these is practical and satisfactory, then the model will be subjected to bootstrapping as described above for outliers. If residual variance changes systematically by value of a covariate (e.g. age) then we will fit the models using iteratively reweighted least-squares, with weighting based on the relevant covariate.

Multiple testing

The issue of multiplicity in outcomes will be addressed by calculating estimated false discovery rates (FDR) for the covariate-adjusted difference between premanifest HD gene carriers and controls. We will perform the FDR analyses at the domain level. (Rigor is not diminished by performing these calculations at the domain level rather than in a single appraisal of the combined domains. Unlike correction for family-wise error rate, FDR calculations depend on the distribution but not on the number of hypothesis test p values considered simultaneously.) One cognitive measure, the CANTAB *inter-extra dimensional shift* task (IED), will be treated as a confirmatory rather than exploratory analysis, based on previous data showing HE differences far from onset. Significance tests will be taken at face value for this test, and it will not be included in the false discovery corrections.

Hypothesis Testing

Hypothesis 1: There is evidence of a disease-related measurable phenotype ~20 years from expected symptom onset in: a) brain imaging; b) cognition; c) neuropsychiatric function; and d) biofluid measures.

A repetition of the cross-sectional analyses performed in HD-YAS 1.0 will be performed, using the additional statistical power provided by the repeated or new subject

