measurements collected in HD-YAS 2.0. Unless otherwise noted, outcomes are continuous or pseudo-continuous measures. By default, we will use general least-square linear models to evaluate possible overall group differences and age interactions between the young adult premanifest HD gene carriers and controls. Within these same models, we will control and test possible CAG-length-driven differences within premanifest HD gene carriers. Covariates will include age, gender, site and age interactions with gender. The main hypothesis of group differences will be evaluated by least-square means.

The primary cross-sectional analyses model will have a nearly identical generic form to that used in the original baseline analysis:

$$y = b_0 + I_{pHD} * (b_1 + b_2 * CAG + b_3 * age + b_4 * CAG * age) + b_5 * age + b_6 * sex + b_7 * age * sex + b_8 * NART + b_9 * EducLevel + r_{subject} + e$$

where y is an outcome variable, $I_{pHD} = 1$ if a participant is from the premanifest HD gene carrier group and 0 otherwise, the b 's are linear regression coefficients, $r_{subject}$ is a subject-specific random effect applicable to participants who have had two measurements, and e is the residual random error term. Both $r_{subject}$ and e are assumed to be independently, identically normally distributed among the participants with 0 mean. (See above for contingencies when these distributional assumptions prove empirically untenable.) Note that NART score (a proxy for estimated baseline IQ) and education level will only be used for cognitive outcomes.

Hypothesis 2: There is evidence of disease-related *longitudinal* change ~20 years from expected symptom onset in: a) brain imaging; b) cognition; c) neuropsychiatric function; and d) biofluid measures.

The longitudinal analyses will build on the above model by adding these further regression terms:

$$a_0 * follow-up + I_{pHD} * follow-up * (a_1 + a_2 * CAG + a_3 * age + a_4 * CAG * age) + follow-up * (a_5 * age + a_6 * sex + a_7 * age * sex + a_8 * IQ,)$$

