where the regression coefficients a. estimate the longitudinal influence of follow-up time with the covariates listed in the original cross-sectional model. One other difference between the cross-sectional and longitudinal analyses is that the cross-sectional analysis will use age at each visit as a covariate, whereas the longitudinal analysis will use age at baseline. This is because changes of age with follow-up and length of follow-up are redundant measures. A readily interpreted assessment of observed longitudinal change with follow-up requires that the age term in the model remains constant.

Boundary Shift Intervals (BSI) measures of MRI volumetric change will require a modification to the above longitudinal model, since these are a direct estimate of change between two MRI scans. Boundary shift volumes will be divided by time between the MRI scans, and the resultant statistic will be used as a volume change rate. This volume change rate will be the outcome variable, y, subjected to analysis.

$$y = b_0 + I_{pHD} * (b_1 + b_2 * CAG + b_3 * age + b_4 * CAG * age) + b_5 * age + b_6 * sex + b_7 * age * sex + b_8 * IQ + e$$

The age term in this BMI model again represents baseline age for the participants, to avoid confounding of changing age and follow-up time in the study. Since there will at most a single BMI measure per participant, the model will contain only a simple residual error term. No subject-specific random effects are estimable.

Hypothesis 3: Early pathological events lead to impairment in isolated functional domains such as cognitive flexibility.

Statistical analyses will only examine potential associations between early pathological events and functional impairment. Issues of causality will remain the subject of logical scientific conjecture. Analyses will be limited to combinations of pathological measures and functional measures that demonstrate differences between the HD gene carriers and controls, per the mixed model analyses described above to address Hypotheses 1 and 2.

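### The SAP's Hypothesis 1 model has no retest term, so a shift shared by both groups on repeat testing biases the carrier CAG coefficient in the direction of the shift

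*SAP*

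**What the plan says.** SAP, Hypothesis 1, repeats the baseline cross-sectional analysis on HD-YAS 1.0 and 2.0 data together, "using the additional statistical power provided by the repeated or new subject" measurements. Returners contribute two records joined by an intercept that "is a subject-specific random effect applicable to participants who have had two measurements".

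The covariate sentence reads: "Covariates will include age, gender, site and age interactions with gender". The formula (b0 to b9) has carrier status and its interactions with CAG, age and CAG x age, then age, sex and age x sex, with NART and education for cognitive outcomes only. Neither the sentence nor the formula contains a visit, wave, follow-up or prior-exposure term.

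On the age variable, the Hypothesis 2 text says that "the cross-sectional analysis will use age at each visit as a covariate, whereas the longitudinal analysis will use age at baseline".

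On the use of the model: "Within these same models, we will control and test possible CAG-length-driven differences within premanifest HD gene carriers".

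On the cohort: "Approximately 4.5 years after baseline 57 premanifest HD gene carriers (89% retention) and 45 healthy controls (67% retention) returned for a follow-up visit", and "An additional 23 new participants were recruited: 9 premanifest HD gene carriers and 14 controls". The SAP's Measures section says that most measures were carried over unchanged from baseline. Protocol section 3.1 describes carriers with a baseline disease burden score (DBS) of at most 240. Protocol section 6 requires CAG of at least 40, and a DBS below 240 for new carriers.

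**The concern.** In this model, age and its interactions are the only fixed effects that change between a returner's two records. If both groups score differently the second time for a reason unrelated to disease, such as practice on the same tasks or assay drift, the model has only age to explain it. Part of the shift therefore becomes a false age slope, which is then applied to age differences between people.

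Among carriers the DBS cap ties age to CAG. The documents do not give the DBS formula. If it is taken as (CAG - 35.5) x age, the cap allows age up to 240/4.5 = 53 at CAG 40, 240/7.5 = 32 at CAG 43 and 240/9.5 = 25 at CAG 45. Carriers with longer CAG are therefore younger. The CAG coefficient offsets the false age slope and takes the sign of the shift.

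What is at stake is the within-carrier CAG test. For cognition, a practice gain would hide a true adverse CAG effect or produce a spurious protective one. Looking like disease would take an adverse shared shift, such as assay drift. The SAP's multiple-testing section applies false discovery control only to the carrier-control difference, so the CAG test has no stated multiplicity control.

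**Working it through.** **1. The plan's own figure.** Protocol section 8 states 80% power for 0.53 SD with 60 per group and 5 covariates. Taking the covariates off the sample leaves 57.5 per group and df 113. The noncentrality is 0.53/sqrt(2/57.5) = 2.84, giving 80.4%. For the partial correlation of 0.36 in 60 carriers, 0.36/sqrt(1 - 0.36^2) x sqrt(55) = 2.86 with df 53 gives 80.2%. Both reproduce. They describe the baseline design, and the documents give no figure for the pooled H1 model.

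**2. Records pooled (SAP, The Cohort).** Carriers: 64 + 57 + 9 = 130. Controls: 67 + 45 + 14 = 126. Of these 256 records, 57 + 45 = 102 are repeats and 154 are first tests.

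**3. Assumed inputs.** The documents do not give the shared shift (taken as 0.1-0.5 SD), the within-person correlation rho (0.5-0.9), the CAG distribution or the baseline age range. The check applies the DBS cap as above, centres CAG and age, sets every group, age and CAG effect to zero, and omits NART, education and site.

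**4. False age slope.** If a 0.3 SD shift over 4.5 years were read wholly as ageing, the slope would be 0.3/4.5 = 0.067 SD per year. Generalised least squares on the H1 model, with a CAG-age correlation of -0.38, gives:
- controls: 0.015, 0.022 and 0.040 at rho 0.5, 0.7 and 0.9, or 22% to 59% of 0.067;
- carriers: 0.021, 0.030 and 0.047, or 31% to 71%.

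**5. False CAG slope.** In the same setting it is +0.044, +0.060 and +0.086 SD per repeat at rho 0.5, 0.7 and 0.9. Without the cap (correlation near 0) it is about 0.001-0.002, which confirms that the cap is the link.

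**6. Rejection of the two-sided 5% CAG test.** With z = bias/SE, the rate is 1 - Phi(1.96 - z) + Phi(-1.96 - z). Averaged over simulated designs:

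| Shift (SD) | CAG-age correlation | rho 0.5 | rho 0.7 | rho 0.9 |
|---|---|---|---|---|
| 0.1 | -0.38 | 5.4% | 5.7% | 6.5% |
| 0.2 | -0.38 | 6.5% | 7.7% | 11.0% |
| 0.3 | -0.38 | 8.4% | 11.1% | 18.7% |
| 0.3 | -0.41 | 9.4% | 12.6% | 21.5% |
| 0.5 | -0.38 | 14.5% | 22.2% | 41.3% |
| 0.5 | -0.41 | 17.2% | 25.5% | 45.3% |

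At correlation -0.32 and rho 0.7 the rates are about 9% (0.3 SD) and 15% (0.5 SD). At -0.38 and 0.3 SD the joint test of CAG and CAG x age rejects 7.6%, 9.7% and 15.4%. Over all the CAG distributions tried, the 0.3 SD rate runs from 5.9% to 29.5%.

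**7. Direction and power.** At correlation -0.32, rho 0.7 and a gain of 0.3 SD, 8.0% of null tests find longer CAG better and 0.7% find it worse. An upper tail of 8.0% means 1.96 - z = 1.405, so z is about 0.555. For a true effect of -0.2 SD per repeat, power without a shift is about 61%, so 0.2/SE = 1.96 + 0.28 = 2.24. With the shift this becomes 2.24 - 0.555 = 1.685, and Phi(1.685 - 1.96) = 39%, in line with the 40% computed directly.

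**8. With a first/repeat indicator.** The CAG bias becomes 0.000. In 500 REML simulations with a 0.3 SD shift, rejection falls from 10.6% to 6.2% (rho 0.7) and from 18.0% to 5.8% (rho 0.9). The unmodified model with no shift gives 6.4%, and Monte Carlo error near 5% is sqrt(0.05 x 0.95/500) = 1.0 point.

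**9. Carrier-control contrast.** At 0.3 SD its bias is 0.01-0.055 SD and its rejection rate 5.4-6.6%.

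**The case against.** The strongest reply is that this is not H1's main test. The SAP evaluates the group difference by least-square means, the false discovery procedure is defined for that difference, and Hypothesis 3 selects its measures on it. That contrast is much less affected because both groups are retested. This stands, and it sets the weight of the point.

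Second, the Hypothesis 2 model already handles a shared shift: it adds a0 x follow-up, fixes age at baseline and keeps the CAG terms. This also stands. But H1 reports its own CAG test from its own fit, and nothing in the SAP makes the Hypothesis 2 estimate replace it.

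Third, a reader might infer that practice effects would manufacture evidence of a disease phenotype. The documents do not support that. A practice gain makes longer CAG look better, and false positives in the disease direction fall below 2.5% (0.7% in step 7). A disease-like artefact needs an adverse shared shift, of which the documents give no evidence. For imaging, the protocol's Imaging assessment section keeps the baseline 3T scanner.

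Fourth, every input that sets the size is assumed, and at 0.1 SD the inflation is negligible. That is correct, so material inflation is possible but not shown. The SAP also does not say which CAG test or centring it will use.

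**Conclusion.** The point holds for H1's within-carrier CAG test. The H1 formula cannot separate a shared retest shift from ageing, and the DBS cap carries part of that error into the CAG coefficient. With a CAG-age correlation of about -0.3 to -0.4 and rho 0.5-0.9, the two-sided rejection rate is about 5-6.5% for a 0.1 SD shift, 7-22% for 0.3 SD and 12-45% for 0.5 SD. For cognition the likelier harm is loss of power against a true adverse CAG effect, from about 61% to 40% in the setting of step 7.

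Two broader readings fail. The whole shift does not pass into the age slope: roughly 20-70% does. The main H1 group comparison is not invalidated. This is a cheap improvement to a secondary H1 test, and it matters only if a shared shift well above 0.1 SD is plausible for the outcome concerned.

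**What to change.** Add one fixed effect to the H1 model, common to carriers and controls: 0 for a participant's first assessment (all HD-YAS 1.0 records and the 23 new participants), 1 for a repeat. Splitting age into age at first assessment plus time since first assessment does much the same, because the gap is about 4.5 years. Where drift between waves is more plausible than practice, as for assays, an indicator for wave should be considered as well. The 23 new participants, first tested at HD-YAS 2.0, are what separate retest from calendar effects.

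The cost is one parameter and a CAG standard error about 2-5% larger (for example 0.0858 to 0.0880, or 2.6%). The common age slope would then rest mainly on differences between people, so some age information is given up if there is truly no shared shift.

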### 3.1 Primary Objective

To highlight the earliest timepoint to target intervention, prior to widespread neuronal damage with the aim of delaying or preventing the onset of symptoms. We will determine whether young adult gene carriers with a disease burden score (DBS) at baseline  $\leq 240$  (Penney et al. 1997) in the Huntington's Disease Young Adult Study exhibit longitudinal differences in:

- Regional brain volumes;
- Structural brain connectivity;
- Functional/effective brain connectivity;
- Grey matter and white matter microstructure;
- Myelination;
- Mutant huntingtin levels in the CSF;
- Cognition;
- NfL in CSF and blood,
- Structural myelin measures in deep and superficial cortical layers;
- Functional measures in deep and superficial cortical layers during cognitive tasks and at rest;
- Coherence between cortical layer structure and function.

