## 6 ELIGIBILITY CRITERIA

### Inclusion Criteria

Healthy controls as well as young adult HD gene expansion carriers will be enrolled.

For the **Healthy Control** group, participants eligible are persons who meet the following criteria:

- a. Are capable of providing informed consent and
- b. Are capable of complying with study procedures and
- c. Are aged between 18-47 years old and
- d. Have no known family history of HD (gene negative); or
- e. Have known family history of HD but have been tested for the huntingtin gene CAG expansion and are not at genetic risk for HD (CAG < 36\*) (family control or community control)

For the **Young Adult Premanifest HD** group, participants eligible are persons who meet the following criteria:

- a. Are capable of providing informed consent and
- b. Are capable of complying with study procedures and
- c. Are aged between 18-47 years old and
- d. Have CAG expansion  $\geq 40$ ;
- e. New participants must have a DBS  $< 240$

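### The H1 cross-sectional model adjusts for age only linearly, and the DBS cap ties long CAG to young age in carriers, so ordinary age curvature may be misread as a within-carrier CAG x age effect.

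*SAP*

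**What the plan says.** SAP, Hypothesis Testing, Hypothesis 1, on adjustment: "Covariates will include age, gender, site and age interactions with gender". In the formula, age appears as b5 (all participants), b7 (with sex) and, in carriers only, b3 (age) and b4 (CAG x age). There is no squared, spline or other non-linear age term.

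The CAG terms are tested as well as adjusted for: "we will control and test possible CAG-length-driven differences within premanifest HD gene carriers". The headline test is different: "The main hypothesis of group differences will be evaluated by least-square means". The false discovery rates under Multiple testing are calculated for that group difference.

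On the age scale, "the cross-sectional analysis will use age at each visit as a covariate, whereas the longitudinal analysis will use age at baseline".

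Under Violation of model distribution assumptions, the SAP covers skewed residuals, floor and ceiling effects, and unequal variance. The polynomial option listed there transforms the outcome, not age.

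On selection, protocol section 3.1 defines the original cohort as "young adult gene carriers with a disease burden score (DBS) at baseline" of at most 240. Section 6 adds "New participants must have a DBS" below 240, "Have CAG expansion" of at least 40, and "Are aged between 18-47 years old and". The DBS formula is not printed.

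**The concern.** A cap on a score built from age and CAG leaves few carriers who are both older and long-repeat. In those who remain, CAG falls with age. Write this as CAG ≈ k - m·age. Then CAG x age ≈ k·age - m·age², so once linear age is in the model, CAG x age carries information about age squared.

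If an outcome follows a normal curve over ages 18-47, such as maturation followed by decline, the straight line misses it and b4 picks up part of it. The controls could identify the curve, but the model gives them only a line.

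The bias in b4 has the opposite sign to the curvature. It can therefore imitate a disease-burden effect or hide one, depending on the outcome.

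At stake is the within-carrier reading. The SAP tests CAG-driven differences, and protocol section 8 plans to test the influence of disease burden among the CAG-expanded. With roughly 70 outcomes, and no FDR planned for b2 or b4, a significant CAG x age result could not be told apart from ordinary ageing.

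**Working it through.** **The plan's own figure.** Protocol section 8 gives 80% power for 0.53 SD with 60 per group, alpha 5% and 5 covariates. A noncentral t with variance factor 1 + 5/(2·60 - 8) = 1.045 gives 80.4%, so the figure is reproduced. It does not bear on the shape of the age effect and is used here only for alpha.

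**Inputs from the documents.** Rows: carriers 64 + 57 + 9 = 130, controls 67 + 45 + 14 = 126, total 256. CAG is at least 40, the DBS cap is 240, and entry age is 18-47.

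**Assumptions, because the documents do not give them.**
- DBS = age x (CAG - 35.5).
- Baseline age uniform on 18-40, 18-42 or 18-47.
- CAG geometric, rounded normal or uniform.
- Within-person correlation (ICC) 0.5 or 0.8.
- Two-sided tests.
- The same quadratic age curve in carriers and controls, explaining 0-10% of curvature-plus-residual variance.
- No true CAG effect.

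**Step 1: what the cap does.** Maximum age = 240/(CAG - 35.5). This gives 240/4.5 = 53.3 at CAG 40, 240/6.5 = 36.9 at CAG 42, 240/8.5 = 28.2 at CAG 44 and 240/10.5 = 22.9 at CAG 46. The induced age-CAG correlation in carriers is about -0.3 to -0.56.

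**Step 2: false-positive rate for b4, two-visit H1 model.** Generalised least squares with a subject effect, baseline age 18-42:

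| CAG distribution, ICC | 0% | 1% | 2% | 5% | 10% |
|---|---|---|---|---|---|
| Geometric, 0.5 | 5.0% | 7.6% | 10.4% | 19.2% | 34.7% |
| Geometric, 0.8 | 5.0% | 9.3% | 13.9% | 28.0% | 49.9% |
| Normal, 0.5 | 5.0% | 9.3% | 13.9% | 28.3% | 51.2% |
| Normal, 0.8 | 5.0% | 12.0% | 19.4% | 41.2% | 69.0% |

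Other choices of age and CAG distribution extend the lower end. Overall the range is about 9-19% at 2% curvature, 14-41% at 5% and 28-69% at 10%. With one observation per person (66 carriers, 59 controls) the rates are 7-11%, 11-21% and 17-36%. The joint test of b2 and b4 is less inflated, at 7-9%, 9-16% and 14-29% with one observation per person.

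**Step 3: is the cap the cause?** With the cap removed (correlation 0.00, one observation per person), the b4 rate is 5.2-6.9% for 1-10% curvature. The cap drives the bias.

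**Step 4: the main group test.** With one observation per person, the least-square-means contrast rejects 5-6% of the time at 1% curvature, 6-9% at 5% and 7-13% at 10%.

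**Step 5: with one shared age-squared term.** Under quadratic curvature the b4 test returns to 5%. Its standard error grows by about 3-8% in the two-visit model and 5-14% with one observation per person. A true effect with 80% power has a standardised size of 1.96 + 0.84 = 2.80. Dividing by 1.04 gives 2.69 and power of about 77%; by 1.08, 2.59 and about 74%; by 1.14, 2.46 and about 69%.

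**Step 6: the longitudinal models.** With baseline age A and follow-up t, c(A + t)² = cA² + 2cAt + ct². The change part is linear in A, so the follow-up x age term (a5) absorbs it. The t² part is nearly constant at about 4.5 years and goes into a0. For BSI, change divided by time is c(2A + t), which the linear age term absorbs. Simulated rates for a4 were 5.0-5.3%.

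**The case against.** The strongest reply is that the SAP's declared main test is the group contrast, not b4, and that contrast is only mildly distorted. This stands.

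Second, the size is conjecture. The documents give no curvature for any outcome, and for questionnaires, functional scales or mHTT a 5-10% quadratic age effect may be unrealistic. This also stands: the rates are conditional, and the case is for guarding against a possibility, not for a demonstrated error.

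Third, the model deliberately keeps nearly the same form as the baseline analysis so that the two can be compared, and an extra term costs power. That is a fair reason to keep the model as written and add a sensitivity analysis. It is not a reason to have no check at all.

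A reader might infer that the same problem runs through the longitudinal CAG terms (a2, a4), the BSI model and the H5 trial-size screen. The documents do not support this. Those models use baseline age, and a quadratic curve is absorbed as shown in step 6. The bias would arise only if the rate of change were itself curved in baseline age, which is a stronger assumption.

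A reader might also infer that every model is affected. That is not so. The H5 effect-size models have follow-up time as their only fixed effect, and the cross-sectional biomarker formula under H3, which H4 reuses, has no CAG x age term. In the H3 models that do contain CAG x age, it is a covariate and the tested term is the pathology measure.

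**Conclusion.** The point holds for the H1 cross-sectional model. Its straight-line age adjustment, combined with selection on DBS, leaves the within-carrier CAG x age test (b4), and more weakly the CAG term (b2), open to contamination by ordinary age curvature. Nothing in the SAP would detect this.

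The inflation ranges from none, with no curvature, to about 9-19% at 2%, 14-41% at 5% and 28-69% at 10%, against a nominal 5%. These figures rest on the assumed DBS formula, the age and CAG distributions, the within-person correlation, and a curve shared by carriers and controls. The direction of the problem is secure; its size in any given outcome is unknown. The documents do not show that a false CAG x age effect will be reported, only that one could be and would go unrecognised.

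The primary group comparison largely survives, so this is an inexpensive improvement to a planned test and not a flaw in the main result.

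**What to change.** In the SAP, add a centred age-squared term, or a low-df spline in age, common to carriers and controls, to the H1 model. At minimum, pre-specify it as a sensitivity analysis that any reported CAG or CAG x age effect must survive. State that linearity in age will be checked in the controls, where CAG plays no part.

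Add the same term to the carrier-only H3 and H4 models of H1 form that contain CAG x age. There the curve must be estimated from carriers alone; these models were not simulated.

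A product of follow-up with baseline age squared in H2, or baseline age squared in the BSI model, is needed only if the rate of change is suspected to curve with baseline age.

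The cost is SAP wording and one or two degrees of freedom out of about 256 rows, using data already collected. The b4 standard error becomes roughly 3-8% larger in the two-visit H1 model, and up to 14% larger with one observation per person. A true CAG x age effect with 80% power would then have about 74-78% (2.80/1.03 = 2.72, about 78%; 2.80/1.08 = 2.59, about 74%), or about 69% in the worst single-observation case.
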